### **Study population**

This study was a randomized controlled clinical trial with a split- mouth study design. Thirty systemically healthy chronic periodontitis (CP) patients, 13 male and 17 female, age  $38.00 \pm 10.12$  years, range 22 – 64 years were recruited from the Department of Periodontology and Oral Medicine, School of Dental Medicine, University of Belgrade. The study protocol was approved by the Ethics Committee of the School of Dental Medicine, University of Belgrade (36/11) and is in compliance with Helsinki Declaration. After being informed of the research methods, all the participants submitted written consent for the enrolment in the study. The study was registered at ClinicalTrials.gov as “NCT04178590”.

The patients were enrolled in the study according to the following inclusion criteria: adults (age between 20 and 75 years), without systemic and/or other oral disease or ongoing drug therapy, which might have an impact on the clinical signs and symptoms of periodontitis, the presence of minimum 6 teeth per quadrant, at least two teeth with periodontal probing depth (PPD)  $\geq 5\text{mm}$  and minimum clinical attachment level (CAL) 3 mm in each quadrant, and a horizontal bone loss, no involvement of furcation degree II or III of both quadrants of the mandible or maxilla, confirmed by full-mouth radiograph images.

Patients who underwent antibiotic therapy during the last 6 months or had initial and/or surgical periodontal treatment within last 12 months, patients with diabetes or in need of long-term use of anti-inflammatory and immunosuppressive medication, current or former smokers, as well as women who are pregnant or lactating, were excluded from the study.

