## **Periodontal examination**

Immediately before the first treatment, as well as at 1, 3 and 6 months, periodontal examinations were carried out by the same examiner. The examination was conducted on all teeth and tooth sites, except the third molars and the tooth sites associated with furcation involvements of II and III degree (Hamp et al. 1975). To identify disease progression, certain variables were recorded from the mesio-buccal, mid-buccal, disto-buccal, disto-lingual, mid-lingual, and mesio-lingual surfaces of each tooth: clinical attachment level (CAL), gingival margin level (GML), periodontal probing depth (PPD), bleeding on probing (BOP), and plaque index (PI). The examiner, a specialist in periodontology, performed and noted down all the recordings. The examiner had previously obtained the adequate level of competence and reproducibility skills according to the various clinical parameters and indices which were going to be utilized (Polson 1997). To avoid blood contamination, GCF collection was conducted one day after clinical examination, after non-surgical periodontal treatment.

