## **Preparation of i-PRF**

Blood samples were taken into two 10 ml tubes and prepared for i-PRF preparation. The whole blood without anticoagulant was then centrifuged at 700 rpm for 3 min ( $60\times g$ ) at room temperature

by a Duo Centrifuge (Process for PRF, Nice, France). The upper liquid layer was taken as i-PRF using a syringe. The i-PRF was applied in one quadrant (treatment group) of the chosen jaw (mandibula or maxilla), whereas the physiological saline was inserted in the opposite side (control group). Treatment allocation was decided by a toss of a coin. i-PRF was enabled to hold for a longer time by applying it into periodontal pockets through perforations at the point of interdental space on individually formed occlusal splints. After 15 minutes the splint was removed.

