Effect of Injectable Platelet-Rich Fibrin (i-PRF) in Initial Treatment of Chronic Periodontitis

- **NCT04178590**
- **26 April, 2020**

Statistical analysis

Statistical Package for Social Science (SPSS software package, version 26.0; SPSS Inc., Chicago, IL, USA) was used for all the data analyses. For numerical data, mean values, medians, standard deviations (SD) and ranges were used for description. The distributions of all outcome values were examined using the Kolmogorov–Smirnov normality test and depending on the distribution, measurements at baseline and at each follow-up between two treatment groups were compared using paired Student's t-test or Wilcoxon signed-rank test. Comparisons within each treatment group for all the measurements were done by repeated measures ANOVA with Bonferroni correction or Friedman and Wilcoxon signed-rank test. Univariate and multivariate logistic regression models were used to assess the predictors of difference between treatment groups. Univariate and multivariate linear regression models were for the predictors of primary outcome (CAL) at 6 months. The differences were considered as significant when the p value was <0.05 . Study power was calculated using DSS Research, for primary outcome (CAL) at 6 months and it was above 90%.

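### In this split-mouth trial the planned logistic predictor models either do not test what modifies the i-PRF effect or lose power; regressing the within-patient CAL difference answers the question directly

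*SAP*

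**What the plan says.** The Protocol (Study population) states: "This study was a randomized controlled clinical trial with a split- mouth study design". It reports "Thirty systemically healthy chronic periodontitis (CP) patients, 13 male and 17 female". Under Preparation of i-PRF, "The i-PRF was applied in one quadrant (treatment group) of the chosen jaw", with saline on the opposite side, and "Treatment allocation was decided by a toss of a coin". Every patient therefore contributes one treated and one control side.

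The SAP (Statistical analysis) recognises this pairing for the main comparison: "measurements at baseline and at each follow-up between two treatment groups were compared using paired" tests. It then adds two sets of predictor models:

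- Logistic: "Univariate and multivariate logistic regression models were used to assess the predictors of difference between treatment groups".
- Linear: "Univariate and multivariate linear regression models were for the predictors of primary outcome (CAL) at 6 months".

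The logistic sentence names no binary outcome. Neither sentence gives the unit of analysis (patient, side, tooth or site), the predictors, or any handling of the pairing. The Protocol contains no regression plan that fills the gap.

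**The concern.** A logistic model needs a binary outcome, and the choice of outcome decides what the model can show. Two readings are possible.

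- **Reading A: treatment group is the outcome.** It is the only binary variable the sentence mentions. Patient-level factors are then balanced between the groups by design. Side-level factors only describe how the two sides differ.
- **Reading B: a dichotomised per-patient difference is the outcome**, for example whether the i-PRF side did better by some margin. This addresses the natural question, but it discards information and no cut-point is given.

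Under A, a factor that truly alters the benefit of i-PRF can be reported as unrelated, and in the multivariate model a merely prognostic factor can be reported as a predictor of the treatment difference. Under B, a real modifier is missed more often than it need be.

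The linear models raise a narrower issue. If both sides enter as independent rows, the standard errors ignore the correlation within a patient.

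**Working it through.** **Inputs.** From the documents: 30 patients, hence 30 pairs or 60 sides; one side per patient in each group; significance at p < 0.05 (two-sided assumed). The documents give no modifier slope, cut-point, mean effect or within-patient correlation ρ. Every such value below is an assumption, shown over a range.

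**The plan's own figure.** The SAP states power above 90% for 6-month CAL but gives no effect size or SD, so it can be neither reproduced nor refuted. It does not concern the predictor models. It serves only as a scale: a paired t-test with 30 pairs needs a mean difference of about 0.61 SD of the differences for 90% power.

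**Step 1. Reading A, univariate.** Let T = 1 for the i-PRF side and 0 for the control side, and let x be a patient-level factor with the same value on both sides. At intercept 0 and slope 0 every fitted probability is 1/2. The score for the slope is Σ x(T − 1/2), and each patient contributes x(1/2) + x(−1/2) = 0. The likelihood is concave, so the estimate is exactly zero however strong the modification. Simulation agrees: the largest absolute coefficient was about 2.5 × 10⁻¹⁶, with 0% rejections.

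**Step 2. Reading A, that side's 6-month CAL added (Wald test).** The coefficient need no longer be zero, but it does not measure modification. With 30 pairs and a mean effect of 1.0 SD of the difference:

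| Factor | ρ = 0.3 | ρ = 0.5 | ρ = 0.7 |
|---|---|---|---|
| Pure modifier (opposite slopes on the two sides) | about 0% | about 0% | about 0% |
| Prognostic only (0.5 total SD per predictor SD), modifies nothing | about 30% | about 20% | about 8% |

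The second row depends on the mean effect. It rises to 59 / 53 / 33% at 1.5 SD; at 0.5 to 0.61 SD the flag rates were low (0 to 5.5%). A modifier acting on the treated side only is also partly prognostic; it was flagged in 18 / 11 / 2% at 1.5 SD. By contrast, in a scenario at ρ = 0.5, regression of the within-patient difference flagged a prognostic-only factor in 4.9% of trials.

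**Step 3. Reading B.** Model: difference = slope × z + N(0,1), n = 30, 10,000 trials per slope.

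| Slope (residual SD per predictor SD) | Linear regression of the difference | Median-split logistic, Wald |
|---|---|---|
| 0.3 | 34% | 19% |
| 0.4 | 54% | 30% |
| 0.55 | 79% | 51% |
| 0.7 | 93% | 70% |

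A likelihood-ratio test narrows the gap (26 / 40 / 61 / 78%) without closing it.

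**Step 4. Linear models, if 60 sides are pooled as independent.**

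- For a patient-level predictor, naive SE / true SE = 1/√(1+ρ), so the type I error is 2[1 − Φ(1.96/√(1+ρ))].
- For a treatment term, naive SE / true SE = 1/√(1−ρ).

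| ρ | Patient-level SE ratio | Type I error | Treatment SE ratio |
|---|---|---|---|
| 0 | 1.00 | 5.0% | 1.00 |
| 0.3 | 0.88 | 8.6% | 1.20 |
| 0.5 | 0.82 | 11.0% | 1.41 |
| 0.7 | 0.77 | 13.3% | 1.83 |

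Simulation gave 8.2–8.7 / 10.7–11.2 / 13.1–13.6% for the three positive correlations. Adding that side's baseline CAL nearly removes the error (5.5–7.2%) only if the patient effect is identical at baseline and 6 months. If those effects correlate 0.5 to 0.7, 7.6–14.0% remains. One row per patient gave 4.7–5.2%. A mixed model with a random patient intercept gave 3.9–5.6%, with a treatment SE ratio of 0.96–1.02.

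**The case against.** The strongest reply is that the SAP never mentions effect modification, age or sex. If group was the outcome and only side-level variables were entered, no misleading patient-level result would arise. That is correct, and the documents do not show which reading was used. But such a model would only describe how the sides differ; it would not say what predicts the size of the treatment difference.

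Second, reading B is valid, so the issue there is efficiency. This also stands. The gain assumes normal residuals, whereas the SAP allows for non-normal outcomes, and at a slope of 0.3 even linear regression detects only 34%.

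Third, the linear models may have used one row per patient or a separate model for each side, in which case nothing is wrong. Even with pooling, the coefficients are not biased, and the error in a treatment term is conservative and arises only if such a term was entered.

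A reader might infer more than this:

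- **That the main treatment comparison ignores the pairing.** It does not; the SAP specifies paired tests.
- **That the logistic models are blind to every patient-level factor.** This is exact for the univariate model under reading A only. The multivariate model can flag factors, including ones that modify nothing.
- **That the linear models are wrong as planned.** The documents do not say that both sides were pooled.

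**Conclusion.** The point holds for the secondary predictor models only. On either reading, the logistic models serve the question worse than regression of the within-patient difference does. With group as outcome, the univariate result for a patient-level factor is zero by algebra, which needs no assumption; the multivariate coefficient answers a different question, and how often it misleads depends on the assumed mean effect, prognostic strength and correlation. With a dichotomised difference, the loss is about 15 to 28 percentage points of detection (34 − 19 = 15 at slope 0.3; 79 − 51 = 28 at slope 0.55), for a median split, a Wald test and normal residuals.

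For the linear models the finding is conditional. Only pooling 60 sides as independent gives wrong standard errors, with false predictors in about 8 / 11 / 13% of trials at assumed correlations of 0.3 / 0.5 / 0.7. It is worth correcting because the remedy is cheap, but it does not bear on the paired result for CAL.

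**What to change.** 1. In place of the logistic models, fit a linear regression of the within-patient difference in 6-month CAL (i-PRF side minus control side, one row per patient). Use a short, stated list of patient-level baseline factors, kept small for 30 patients, and include the within-patient baseline CAL difference as a covariate. The detection figures above were obtained without that covariate.
2. If a responder outcome was intended, define it with its cut-point and keep it as a supplementary analysis.
3. For the 6-month CAL models, state the unit of analysis and the predictors. If both sides enter, use a linear mixed model with a random patient intercept and fixed terms for treatment and that side's baseline CAL. Because CAL was recorded at six surfaces per tooth (Protocol, Periodontal examination), add nested side and tooth effects if site-level rows are used. If one row per patient was used, say so; no change of method is needed.

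Cost: revised SAP wording and, where a model changes, a re-run on existing data in the SPSS package already named. No new data are needed. The mixed model is slightly more complex to report than ordinary regression.
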